1.0 Objectives

1.1 Overview

The experience of hematopoietic cell transplantation (HCT) among Adolescents and Young Adults (AYAs) with cancer is particularly difficult because age-related developmental challenges of identity, relationships, and vocation may add to the burden of cancer. Compared to other age-groups, AYAs have poorer psychosocial outcomes including increased anxiety and depression and poorer adherence to oral immunosuppressive medications. These outcomes may, in turn, predispose AYAs to disease-related morbidity and mortality such as graft-versus-host disease (GVHD) and/or cancer-relapse. A potential barrier to improving these experiences may be that AYAs have few opportunities to develop the personal resources needed to handle adversity. We have previously developed the “Promoting Resilience in Stress Management” (PRISM) intervention for AYAs with serious illness. This manualized, brief intervention is delivered in 4, 30-60 minute, one-on-one sessions, followed by a Parent/ Caregiver/ Spouse/ significant other inclusive meeting. It targets skills in stress-management and mindfulness, goal-setting, positive reframing, and meaning-making. All of these skills are associated with improved patient well-being in other populations, and preliminary findings from a recently closed pilot randomized controlled trial among AYAs with newly diagnosed cancer suggest PRISM is associated with improved health-related quality of life. This study will build on our prior experience and fill a critical knowledge gap regarding PRISM’s impact among AYAs receiving HCT. Thus, we will conduct a multi-site randomized controlled trial among N=70 AYAs (n=35 PRISM and n=35 usual care; ages 12-24 years), with the primary trial outcome of patient-reported symptoms of anxiety and depression. Secondary outcomes will include the cost-effectiveness of the intervention in this population and the impact of the intervention on parent well-being. Exploratory outcomes will assess patient adherence to oral GVHD medications, as well as three biomedical variables associated with psychological distress; heart rate variability (HRV), days to neutrophil engraftment (DNE), and development of acute GVHD. We hypothesize that AYAs who receive PRISM will report fewer mixed affective symptoms, demonstrate better adherence, and show improved biomedical outcomes, while their parents report improved quality of life and psychological distress. We also anticipate the intervention will be cost-effective. In sum, this study offers an opportunity to expand the body of knowledge regarding methodologically rigorous and evidence-based psychosocial interventions and standards of care for AYAs with hematologic and other malignancies. Ultimately, this research has the potential to reduce the burden of cancer in these vulnerable populations.

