1.5 Exploratory Aims

1.5.1 Evaluate the effectiveness of PRISM compared to usual care in promoting adherence to oral GVHD prophylaxis.

Outcome Measures: (i) Medication Electronic Monitoring Systems (MEMS) cap electronic adherence assessments during the remaining 6 months following initial hospitalization for HCT.

1.5.2 Prospectively describe associations between PRISM, patient reported anxiety and depression, and stress biomarkers.

Outcome Measures: (i) Days from HCT to neutrophil engraftment, (ii) prevalence and severity of GVHD (revised Seattle Criteria), (iii) heart rate variability (as measured by the interbeat interval (IBI), (iv) gene expression profile.

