9.9.3 Data Collection Schedule

HRV data and/or blood samples will be collected at clinically relevant and study specific time intervals where possible (**Table 6**). When not possible, HRV and/or blood sample data collection will be scheduled at the patient's convenience, and/or during the next scheduled clinical lab draw. .

Table 6. Biological data collection schedule

Time Point	T1 (Baseline)	T2 (PRISM session #1 OR 1 week post enrollment)	T3 1 month (survey timepoint)	T4 3 months (survey timepoint)	T5 6 months (survey timepoint)
24-hour HRV Recording	X	X	X	X	X
Blood Sample	X		X	X	

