11.5.4 **We will explore the relationship between biomedical variables and patient reported anxiety and depression** through a combination of paired and unpaired t-tests, chi-squared (or Fisher's exact) tests, and linear and logistics regression. DNE will be defined as the number of days from transplant to an absolute neutrophil count (ANC) of >500/mm³ for >3 days. Cumulative incidence and severity of Grade II-IV GVHD will be defined by the revised Seattle Criteria as documented by the patient's clinical provider. HRV will be measured in 24-hour increments using both time and frequency domain parameters as established by the international Cardiology task force guidelines. Means and standard deviations will be compared to published normative data in adolescents. CTRA scores will be divided into two groups (above and below the median). We will perform multivariable analyses, adjusting for age, sex, diagnosis, disease status at the time of transplant, conditioning intensity, and,

immunosuppressive medications/GVHD prophylaxis to examine the association between CTRA biology and HCT outcomes.

11.6 Additional analyses, confounders, and other considerations.

We will conduct interaction modeling and subgroup analyses to explore whether the effect of the intervention is modified by medical covariates, symptom distress, and/or adherence. The rationale for these subgroup analyses is grounded in prior findings suggesting symptoms, adherence, and overall well-being are associated.¹⁴⁰

We will conduct a thorough process evaluation that includes: (a) intervention fidelity; and, (b) satisfaction queries. Multiple comparisons are a concern since we are collecting multiple measures from patients and are interested in several hypotheses. We minimize this problem by specifying a limited number of main hypotheses for each aim. The Benjamini-Hochberg procedure will be used to control the False Discovery Rate criterion at $\alpha=0.05$ to correct for multiple testing in analyses that are not pre-specified.¹⁴¹ Likewise, in manuscripts and presentations, we will report the number of tests performed and interpret results within this context.

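### Section 11.5.4 specifies no between-arm analysis of HRV or CTRA and does not use the baseline recordings as a covariate, although the protocol asks whether PRISM is associated with these biomarkers

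*Combined protocol and SAP*

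**What the plan says.** **The question asked.** Section 1.1 hypothesises that patients given PRISM will "demonstrate better adherence, and show improved biomedical outcomes", and lists HRV, days to neutrophil engraftment and acute GVHD as the biomedical variables. Section 1.5.2 states the exploratory aim: "Prospectively describe associations between PRISM, patient reported anxiety and depression, and stress biomarkers". It names HRV and gene expression among the outcomes. Section 2.2 makes PRISM's association with biomarkers one of four key questions.

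**The data collected.** In Table 6 (section 9.9.3) the row labelled "24-hour HRV Recording" is marked at all five time points, T1 to T5. Blood is drawn at T1, T3 and T4. Both components are optional.

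**The analysis planned.** Section 11.5.4 opens: "We will explore the relationship between biomedical variables and patient reported anxiety and depression". The methods are "through a combination of paired and unpaired t-tests, chi-squared" or Fisher's exact tests, "and linear and logistics regression". The only HRV-specific comparison is "Means and standard deviations will be compared to published normative data in adolescents". CTRA is split at its median, and the one adjusted biomarker model relates CTRA to transplant outcomes.

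**Elsewhere in the plan.** Section 11.1 adjusts every analysis for age and site, and for baseline characteristics that are clearly imbalanced. Section 11.4.1 puts baseline HADS in the primary regression. Sections 11.4.2.1 and 11.4.3 carry that model over to the secondary patient-reported outcomes and the parent outcomes. Section 11.5.4 does not carry it over to the biomarkers.

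**The concern.** The aim links PRISM to the biomarkers, but the analysis section links the biomarkers to anxiety and depression and to transplant outcomes. Randomised arm, the one exposure in this trial protected from confounding, does not appear. The HRV comparison with norms describes how transplant patients differ from a reference group. Any such difference reflects illness, treatment and age, and would be present in both arms.

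Two things are at stake. First, the trial may gather repeated recordings and blood samples and then have no stated analysis that answers its own question. With up to four post-baseline HRV records per patient, any comparison of arms would have to be devised later. Second, HRV and CTRA come from an optional subset of unstated size. Section 3.1 withholds HRV when in-person contact must be minimised, and section 13.1 restricts CTRA to Seattle. In a sample that small, leaving a measured baseline value unused costs precision that could be had for nothing.

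**Working it through.** **1. Is there a biomarker figure to reproduce?** No. Table 7 covers patient- and parent-reported outcomes only. The documents give no sample size, SD, power or detectable difference for HRV or CTRA. The steps below are therefore an illustration under stated assumptions.

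**2. Question against analysis.**

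| Element | Question (1.1, 1.5.2, 2.2) | Section 11.5.4 |
|---|---|---|
| Exposure | PRISM against usual care | HADS symptoms; external norms; CTRA group |
| Randomised arm | Central | Not mentioned |
| T1 value | Collected for HRV and CTRA (Table 6) | No stated use |
| Repeated records | HRV five times, CTRA three times | Handling not stated |

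**3. What T1 adjustment is worth.** Inputs:
- Allocation is 1:1 (section 9.2).
- 35 per arm is the evaluable target for the whole trial (section 11.2), taken here as an upper value for the optional subset. 20 per arm is assumed as a smaller case.
- The T1 to follow-up correlation ρ is assumed to be 0.3, 0.5 or 0.7.
- Two-sided 5% error and 80% power; equal variance at T1 and follow-up; normal approximation.

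Variance of the arm difference relative to a t-test on follow-up values alone:
- T1 as covariate (ANCOVA): 1 − ρ²
- t-test on change from T1: 2(1 − ρ)

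| ρ | ANCOVA | Change score | Variance saved by ANCOVA | Equivalent sample, 1/(1 − ρ²) |
|---|---|---|---|---|
| 0.3 | 0.91 | 1.40 | 9% | 1.10 |
| 0.5 | 0.75 | 1.00 | 25% | 1.33 |
| 0.7 | 0.51 | 0.60 | 49% | 1.96 |

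A change-score t-test beats a follow-up-only t-test only when ρ exceeds 0.5. ANCOVA is at least as efficient as either at every ρ.

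**4. The same in detectable differences.** In SD units this is (1.960 + 0.842) × √(2/n) × √f, where f is the variance factor above.
- n = 35 per arm: 2.802 × √(2/35) = 0.67 with follow-up only; with ANCOVA 0.64, 0.58 and 0.48 for ρ = 0.3, 0.5 and 0.7.
- n = 20 per arm: 2.802 × √(2/20) = 0.89 with follow-up only; with ANCOVA 0.85, 0.77 and 0.63.

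The gain is modest at ρ = 0.3 and substantial at 0.7. At ρ near zero there is none.

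**The case against.** The strongest reply is that this is silence in an exploratory section, not a wrong analysis. The aim is worded as description, no power is claimed, and the listed methods are broad enough to include a comparison of arms. Most of that stands, and it rules out several stronger readings.

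- **That the analysis rests on t-tests alone.** It does not. Linear and logistic regression stand in the same sentence of section 11.5.4, and section 11.1 already adjusts for age and site.
- **That PRISM gets no fair test.** An unpaired t-test between randomised arms would be unbiased, and it is among the listed methods. Consent to the optional components is sought before randomisation (sections 3.1 and 9.1), so the arms within the subset are still randomised groups. The fault is that no comparison is specified, and one that omits T1 would usually be less precise.
- **That type I error is inflated.** This would follow if repeated records were pooled as independent. With three records per patient and an intraclass correlation of 0.3 to 0.5, the design effect is 1 + 2 × ICC = 1.6 to 2.0, and the true error for a between-patient factor would be about 12% to 17%. But the plan nowhere says that records will be pooled, so this is a hazard to close off and not a finding.
- **That the norms leave out ages 18-24.** The text says only that the data are in adolescents. Their age range is not given.
- **That the norm comparison is offered as the test of PRISM.** It is not. Section 1.6 mentions norms only as a feature of HRV.

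It is also fair to object that ρ is unknown. Enrolment may fall up to four weeks either side of transplant (section 3.2.1.3) and recordings may be moved for convenience (section 9.9.3), so T1 may predict later values only weakly. That limits the size of the gain. It does not supply the missing comparison.

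**Conclusion.** The point holds in a limited form. Section 11.5.4 specifies no between-arm analysis of HRV or CTRA and does not use T1 as a covariate, while sections 1.1, 1.5.2 and 2.2 pose a question that needs both. The comparison with adolescent norms cannot fill the gap. The general rule in section 11.1 would bring T1 in only if it happened to be clearly imbalanced, which is a different reason from its being predictive.

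The size is a 9% to 49% reduction in variance from T1 adjustment. It rests on an assumed correlation of 0.3 to 0.7, equal variances, and a T1 value taken before the intervention can affect it. The figures apply to continuous values and not to CTRA split at the median.

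Severity is low. The aim is exploratory, and neither the primary HADS analysis nor its conclusion is touched. Days to engraftment and GVHD have no baseline value, so the efficiency argument does not extend to them.

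**What to change.** In section 11.5.4:

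1. Add an exploratory between-arm comparison of continuous HRV and continuous CTRA values, adjusted for the T1 value and age group. Add site for HRV only: CTRA is collected at one site, so a site term there cannot be estimated.
2. Use ANCOVA at one named visit, or a repeated-measures model with a patient random effect if several post-baseline visits are used. In a small subset ANCOVA may be all that the data support.
3. Report the arm difference with a 95% confidence interval, labelled exploratory.
4. Where repeated records enter the model relating biomarkers to HADS, account for within-patient correlation.
5. State that the comparison with published norms is descriptive only.

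Engraftment and GVHD are outside this change. The cost is a few lines of plan wording and a little analysis time, with no new data and no added burden on patients.

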9.3.2 Randomization. Patients will be randomized following completion of baseline RPCA surveys. Staff will aim for the RPCA surveys to be completed immediately following enrollment. Baseline surveys will be collected within the first two weeks. If surveys are not completed within this time-frame, staff will return to the participant to confirm interest and offer a digital (or, when requested paper-pencil or interview-based) survey to be completed in real-time. If participants do not complete the survey at that time, they will be removed from the study. For those who do complete the survey, following completion, staff at each site will receive their randomization allocation. They will then return to patients and families to relay this information and create a study calendar outlining survey due-dates and, where relevant, PRISM sessions. Where relevant, PRISM-sessions will be scheduled approximately every other week, beginning within the first week of enrollment.

9.4 Overview and Session Details of Intervention Arm.

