Beginning 2 weeks following the date of discharge from initial HCT hospitalization and for the final duration of the remaining 6 months on study, participants will store prescriptions for their primary GVHD prophylaxis (typically either tacrolimus or cyclosporine), in study-dispensed MEMS bottles and caps. A patient supply kit containing a MEMS cap and bottle will be dispensed to all study participants by the institutional RA no more than 7-10 post discharge. The patient will receive instructions directing them to put their primary GVHD prescription into these bottles and to take their prescription using the MEMS medication bottle. The patient will be instructed that any additional refills of their GVHD prophylaxis required during the study period are also to be added to their MEMS medication bottle. When possible, the study RA will meet with families in person approximately 2 weeks post-discharge to verify new prescription has been dispensed in these bottles and to review procedures. A study coordinator will

contact study participants monthly by phone, email, text or in person to answer any questions or concern the patient may be having.

The following instructions will be included in the patient supply kit:

1. In the next 1 -2 days, please put your main GVHD prophylaxis medication into your MEMS medication bottle. If you are unsure what medicine this is, please check with your study team.
2. Once you have filled your bottle, before you take your next dose of your GVHD medication, please replace the regular cap with the MEMS TrackCap you received in your study kit.
3. All doses of your GVHD medication should be taken from the MEMS medication bottle with the MEMS TrackCap while you are on this study.
4. Please take your GVHD medication exactly as your doctor has ordered.
5. Open the medication bottle ONLY when it is time for you to take your GVHD medication.
6. Close the medication bottle right after taking the GVHD medication.

➤ To refill your GVHD medication while on this study, follow these instructions.

- Only refill your medication when you need to take a dose of your GVHD medication!
 - Open the old bottle and take out a dose of medication.
 - Refilled bottle with your GVHD medication using your prescription bottle from your pharmacy.
 - Replace the electronic Trackcap onto the newly refilled bottle of your GVHD medication.
 - Please do not refill or open your MEMS cap when you are not taking your medicine.

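### Exploratory analyses: CTRA is specified only as a median split (11.5.4), and adherence, recorded after randomisation, is listed as a modifier of the PRISM effect (11.6), so effects within adherence levels can be biased either way

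*Combined protocol and SAP*

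**What the plan says.** **CTRA.** Section 11.5.4 names t-tests, chi-squared or Fisher tests and linear and logistic regression for the biomedical variables in general. For CTRA itself it says: "CTRA scores will be divided into two groups (above and below the median". It gives no reason for the cut. Multivariable models then relate CTRA to HCT outcomes, "adjusting for age, sex, diagnosis, disease status at the time of transplant, conditioning intensity" and immunosuppression or GVHD prophylaxis, which makes six factors. CTRA is an optional component (Section 3.1) collected only in Seattle (Section 13.1).

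**Adherence.** Section 11.6 plans "interaction modeling and subgroup analyses to explore whether the effect of the intervention is modified by medical covariates, symptom distress, and/or adherence". It adds: "The rationale for these subgroup analyses is grounded in prior findings suggesting symptoms, adherence, and overall well-being are associated". No time of measurement is given for any of these modifiers. On timing, Section 9.3.2 says "Patients will be randomized following completion of baseline RPCA surveys", and Section 9.5 starts MEMS recording as follows: "Beginning 2 weeks following the date of discharge from initial HCT hospitalization". Table 5 lists no adherence instrument at baseline or later. Adherence is also an outcome. Aim 1.5.1 is to "Evaluate the effectiveness of PRISM compared to usual care in promoting adherence to oral GVHD prophylaxis", and Section 1.1 says: "We hypothesize that AYAs who receive PRISM will report fewer mixed affective symptoms, demonstrate better adherence, and show improved biomedical outcomes".

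**The concern.** Cutting a continuous score at its median treats everyone on one side as equal and discards the rest of the information. In a small optional sample, a real CTRA association is then more likely to be missed.

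A modifier analysis compares the arms within levels of a third variable. Randomisation protects that comparison only if the treatment cannot have affected the variable. If PRISM changes adherence, PRISM and usual-care patients at the same adherence level are no longer exchangeable. Where adherence is a mediator, part of the PRISM effect is also removed. A reader could take adherence subgroup results for randomised comparisons when they are not.

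**Working it through.** The plan gives no sample size, effect size or power for either analysis, so there is no figure to reproduce. Sizes below are assumptions unless a section is cited.

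**1. CTRA median split**

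Information kept is the squared correlation between the score x and the indicator d that x exceeds its median. For standard normal x:

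- E[x·d] = 1/√(2π) = 0.399, and SD(d) = 0.5
- correlation = 0.399/0.5 = 0.798
- information kept = 0.798² = 2/π = 0.637
- sample-size penalty = 1/0.637 = 1.57

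Simulated values for other shapes: uniform 0.75, t with 5 df 0.54, Laplace 0.50, exponential 0.48.

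Two sample sizes can be drawn from the documents, both assuming that every Seattle enrollee gives blood: 11 per year × 3 years = 33 (Table 3), and 55, the middle of the 50 to 60 in Section 25.0. A third, n=20, stands for partial uptake. Simulated power at an assumed partial correlation of 0.4 (two-sided 5%, linear model), continuous versus split:

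| Covariate terms | n=20 | n=33 | n=55 |
|---|---|---|---|
| none | 43% vs 28% | 66% vs 44% | 88% vs 68% |
| six | 30% vs 20% | 57% vs 38% | 83% vs 62% |
| ten | 21% vs 14% | 49% vs 32% | 79% vs 58% |

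Type I error was 4.6% to 5.6% throughout. The ten-term row is shown because factors such as diagnosis may need more than one term.

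For a binary outcome (assumed odds ratio 2.5 per SD, prevalence 30% to 50%, unadjusted), power is 60–66% versus 43–44% at n=33 and 81–87% versus 62–70% at n=55. With six covariates at n=33 the logistic likelihood-ratio test has type I error of 9% to 11%, so no adjusted power is quoted there.

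**2. Adherence as a modifier**

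The order of events is baseline survey, randomisation, HCT discharge, then MEMS recording. No baseline adherence measure is planned.

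Let d be the PRISM gain in adherence in SDs, and c the within-arm correlation of adherence with HADS. Take a true effect of −3.1 for everyone and SD 6.2 (the MCID and SD in Table 7). In a linear model:

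effect at mean adherence = −3.1 − 6.2 × c × d

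| c | d=0 | d=0.3 | d=0.5 |
|---|---|---|---|
| −0.5 | −3.10 | −2.17 | −1.55 |
| −0.3 | −3.10 | −2.54 | −2.17 |
| 0 | −3.10 | −3.10 | −3.10 |
| +0.3 | −3.10 | −3.66 | −4.03 |

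Shrinkage therefore needs both d > 0 and c < 0. For negative c and positive d it is 18% (0.56/3.1) to 50% (1.55/3.1). In both strata of a median cut the simulated effect is −2.75 to −2.13 over the same cases, a shrinkage of 11% to 31%.

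The sign of the bias depends on the causal structure. Large-sample regressions with a 0.5 SD adherence gain:

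| Structure | Total effect | Effect given adherence |
|---|---|---|
| Adherence lowers HADS | −4.1 | −3.1 |
| Adherence unrelated to HADS | −3.1 | −3.1 |
| Unmeasured factor raises adherence, lowers HADS | −3.1 | −2.2 |
| Unmeasured factor raises both | −3.1 | −4.0 |
| Adherence raises HADS | −2.6 | −3.1 |

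In a separate run where lower HADS itself improves adherence, −3.1 became −2.5.

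Sampling error puts this in scale. The SD of the effect at mean adherence is 1.30–1.49 at n=70, so the largest shrinkage is 1.55/1.49 = 1.0 to 1.55/1.30 = 1.2 SDs. But n=70 is the whole evaluable trial, while adherence monitoring is optional and restricted to allogeneic HCT (Section 3.1). At an assumed n=40 the SD is 1.74–1.99 and the ratio 0.8 to 0.9.

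The interaction coefficient stayed near zero in the structures of the table above. At trial size the false-positive rate of the interaction test was 4.4% to 5.4% with a linear term and 4.6% to 5.2% with a median cut. With a cut at the control arm's 20th percentile it was 4.1% to 4.7%.

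**The case against.** **On CTRA.** Section 11.5.4 does not call the split the only form. It lists linear regression generally, and its multivariable sentence concerns CTRA biology, not CTRA group. Aim 1.5.2 is descriptive and no power claim is contradicted. CTRA was added by an amendment dated 10/3/2019, so earlier Seattle enrollees may lack baseline samples, and at n=20 power is poor under either analysis. If the true relation is a step near the median, the split would do better. All of this stands and keeps the point minor. It does not supply a continuous analysis, which the text never states.

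**On adherence.** Section 11.6 asks whether the effect is modified, and that test keeps its size. The log of changes says adherence was made exploratory for lack of power. Section 11.6 also promises to report the number of tests and to apply Benjamini-Hochberg to analyses not pre-specified. This stands too, but multiplicity control does not address bias from conditioning on a post-randomisation variable.

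A reader might infer that modelling adherence must shrink the PRISM effect once PRISM improves adherence. The documents do not support that. Better adherence must also go with lower HADS, and the rationale in 11.6 states an association without a direction. Section 2.1.1 does suggest one, linking distress to poorer adherence and positive re-appraisal to less distress and better adherence. Shrinkage is therefore the likelier case, but unmeasured factors could reverse it.

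A patient enrolled late and discharged early might reach the MEMS start before randomisation. That would be incidental and is not a planned baseline measure.

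**Conclusion.** Minor, and confined to exploratory analyses.

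(1) The stated CTRA split keeps about 64% of the information under normality and linearity, less if the score is heavy-tailed or skewed, and 75% if uniform. The power loss of about 19 to 21 points at n=33 and n=55 with six terms rests on an assumed partial correlation of 0.4 and full uptake. The actual sample size is unknown and may be lower.

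(2) PRISM effects within adherence levels are not protected by randomisation. They are biased toward zero if PRISM improves adherence and better adherence goes with lower HADS, unchanged if adherence is unrelated to HADS or PRISM does not change it, and biased away from zero if the association is reversed. Under the assumed sizes the shift is at most about one sampling SD, slightly more at n=70.

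Two stronger readings should be resisted. The interaction test is not invalid, since its false-positive rate is not materially affected. The HADS analysis in 11.4.1 and the secondary aims are also not affected.

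**What to change.** **Section 11.5.4.** State that CTRA will be analysed as a continuous score, with linearity checked by plot, and that the median split is for display only. Cost: wording only. The downside is reliance on a roughly linear relation.

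**Section 11.6.** Remove adherence from the effect modifiers. Report it as an outcome under aim 1.5.1 or, with assumptions stated, as a mediator. For symptom distress and medical covariates, whose timing is not given, use baseline values where they exist. Label any analysis by a post-randomisation variable as non-causal. Cost: wording and no new data. The downsides are that a mediation analysis needs assumptions the trial cannot test, and that some post-baseline subgroup analyses become descriptive only.
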